 Syneron Medical Ltd. Confidential	Clinical Study to Evaluate the Safety and Efficacy of the UltraShape Power Device Using the U-Sculpt Power Transducer for Abdominal Fat and Circumference Reduction			
	Protocol #	DHF21621	Rev. Date	April 05, 2016

	7. Subject improvement and satisfaction: Improvement and satisfaction assessment will be performed independently by the subject himself using a pre-defined scale questionnaire. The subjects will answer this questionnaire at each follow-up visit (4wk FU, 8wk FU and 12wk FU)
Efficacy Endpoints	Primary and secondary objectives will be measured using the next efficacy endpoints: 
 1. Fat thickness measurements using Ultrasound device 2. Fat thickness measurements using calibrated Caliper 3. Circumference measurements of the abdominal area using Measuring Tape 4. Investigator satisfaction using a pre-defined scale 5. Subject improvement and satisfaction using a pre-defined scale 6. Photography
Safety Endpoints	
 1. The number, severity and type of any adverse event recorded throughout the study and post treatment (immediate and delayed response) 2. Pain assessment using NSR scale
Statistical Methods	Descriptive statistics will be used to present changes in the assessments along the study course. Circumference measurements and subject assessments' and satisfaction data will be analyzed using two-tailed Wilcoxon Signed Rank test and/or paired t-test (alpha=0.05) to analyze the data difference from baseline and longitudinal change.

INTRODUCTION AND RATIONALE

Background

Adipose tissue is a loose type of connective tissue specialized to store lipids. The majority of lipids stored in adipose cells are triglycerides formed from imported free fatty acids and glycerol. It is not uniformly distributed in the body. The major adipose depot is subcutaneous (about 80% of all body fat).¹ In men it normally represents 15-20% of body weight and in women, 20-25% of body weight. A certain amount of body fat is necessary for normal female reproduction and health. Subcutaneous adipose tissue helps to shape, cushion and insulate the body and provides padding to some organs.

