1. Statistically significant abdominal fat reduction post UltraShape Power treatments as measured by Ultrasound device at Pre Tx.3, 4 weeks, and 8 weeks follow-up (4wk FU and 8wk FU) versus baseline.
2. Statistically significant abdominal fat reduction post UltraShape Power treatments as measured by calibrated Caliper at Pre Tx.2, Pre Tx.3, 4 weeks, 8 weeks and 12 weeks follow-up (4wk FU, 8wk FU and 12wk FU) versus baseline.
3. Statistically significant abdominal circumference reduction post UltraShape Power treatment/s at Pre Tx.2, Pre Tx.3, 4 weeks, 8 weeks and 12 weeks follow-up (4wk FU, 8wk FU and 12wk FU) versus baseline.
4. Investigator satisfaction:
Satisfaction assessment will be performed by the study investigator using a pre-defined scale questionnaire. The investigator will answer this questionnaire at each follow-up visit (4wk FU, 8wk FU and 12wk FU).
5. Subject improvement and satisfaction:
Improvement and satisfaction assessment will be performed independently by the subject himself using a pre-defined scale questionnaire. The subjects will answer this questionnaire at each follow-up visit (4wk FU, 8wk FU and 12wk FU).

Primary and Secondary Efficacy Endpoint

Primary and secondary objectives will be measured using the next efficacy endpoints:

1. Fat thickness measurements using Ultrasound device
2. Fat thickness measurements using calibrated Caliper
3. Circumference measurements of the abdominal area using Measuring Tape
4. Investigator satisfaction using a pre-defined scale
5. Subject improvement and satisfaction using a pre-defined scale
6. Photography

 Syneron Medical Ltd. Confidential	Clinical Study to Evaluate the Safety and Efficacy of the UltraShape Power Device Using the U-Sculpt Power Transducer for Abdominal Fat and Circumference Reduction			
	Protocol #	DHF21621	Rev. Date	April 05, 2016

Primary Safety Endpoint

The number, severity and type of any adverse event recorded throughout the study and post treatment (discomfort (pain), immediate and delayed response).

1. Occurrence of expected post treatment immediate response including erythema and edema and during all study period based on predefined scale (Table 4).
2. Number, severity and type of any adverse event recorded throughout the course of the study.

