Figure 9: Patient positioning during circumference measurements (A) and measuring device position around the abdomen (B)

7. The measurement device should be activated at a constant tension to achieve an exact measurement of the circumference (use measurement device supplied by Syneron only).
8. In order to minimize measurement inaccuracies originating from human error, it is recommended that, whenever possible, the same operator re-measures the patient at approximately at the same hour of day (± 3 hours).
9. Patients should be under fasting for at least 3 hours prior to circumference measurement.

Treatment Procedure

Subjects will receive treatments with UltraShape Power device utilizing the U-Sculpt Power Transducer on the anterior abdomen.

Prior to each treatment measurements of weight, fat thickness (both by Ultrasound and Caliper), and abdominal circumference will be done according to the references from the enrollment visit (Baseline/ prior to Tx.1). Only patients who are eligible for treatment will be allowed to undergo the UltraShape Power procedure.

Enrolled subjects will undergo 3 successive bi-weekly (2 weeks interval) treatments (Tx.1, Tx.2 and Tx.3). Additional three (3) visits in the clinic will be occurred to follow-up the abdominal fat and circumference reduction at visits 4, 5 and 6 (4 weeks, 8 weeks and 12 weeks following last treatment).

 Syneron Medical Ltd. Confidential	Clinical Study to Evaluate the Safety and Efficacy of the UltraShape Power Device Using the U-Sculpt Power Transducer for Abdominal Fat and Circumference Reduction			
	Protocol #	DHF21621	Rev. Date	April 05, 2016

UltraShape Power Treatment Procedure

The subject abdomen will be gathered using reusable straps (supplied by Syneron Medical), to gather the fat area for treatment according to the instruction written in the User Manual.

According to size of the treatment area, the UltraShape Power device will determine the total number of FTZs to be delivered during treatment. While the recommended minimal number of ultrasound FTZs to be delivered per subject at a whole single treatment will be defined / determined by the system according to the subject physical characteristic and treated area size. Prior to admitting the FTZs (pulses) Parker acoustic gel will be applied and on the treated area and used as a coupler agent between the ultrasonic U-Sculpt Power Transducer and the skin surface.

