Perform the UltraShape Power utilizing the U-Sculpt Power Transducer treatment according to the instruction in the User Manual.

Expected post treatment side effects are limited to Erythema (blanchable/non-blanchable), Edema, Heat sensation and pain sensation.

Post Treatment Procedures

1. Pain assessment – immediately after each treatment the subjects will be asked to rank the pain sensation during treatment using Numerical Scale Response (NSR; see Appendix III) for the UltraShape Power procedure
2. Safety aspect will be assessed before and after each treatment:
 - a. Clinical effects - All visible and palpable immediate response will be recorded for the entire treatment area using a 4-point severity scale (Table 4)
 - b. Adverse Events – Record the number, severity and type of any adverse event occurred before, through and after treatments.

Return Visits

All subjects will be requested to return to the clinic at the following time-points during the study in order to assess the clinical performance of the device:

- Visit 4: FU1 – 4 weeks (± 7 days) post last treatment.
- Visit 5: FU2 – 8 weeks (± 7 days) post last treatment.
- Visit 6: FU3 – 12 weeks (± 7 days) post last treatment.

At each return visit the following procedures will be conducted and data recorded:

- Weight.
- Ultrasound fat-thickness measurements.
- Caliper fat-thickness measurements.
- Circumference measurements.

SYNERON CANDELA Syneron Medical Ltd. Confidential	Clinical Study to Evaluate the Safety and Efficacy of the UltraShape Power Device Using the U-Sculpt Power Transducer for Abdominal Fat and Circumference Reduction			
	Protocol #	DHF21621	Rev. Date	April 05, 2016

- Skin assessment for clinical effects due the procedures:
 - Post treatment response and adverse events.
- Photographs as conducted at baseline.
- Satisfaction questionnaire performed by the investigator using the Global Aesthetic Improvement (GAI).
- Completion of the Subject Follow Up questionnaire:
 - Subjective Improvement and satisfaction performed by the subject using the Global Aesthetic Improvement (GAI).
- At the final visit a urine pregnancy test will be performed for women with bearing potential.

DATA ANALYSIS

Recording

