An adverse event (AE) is any adverse change in health or side effect that occurs in a study participant during their participation in the study.

Anticipated Adverse Effects

Following treatment with the UltraShape Power the following local adverse effects could occur (anticipated):

- Purpura
- Blister
- Bruising
- Bullae
- Erosion
- soreness
- First degree burn
- Second degree burn

An adverse event (AE) is any undesired clinical occurrence in a study subject as indicated by signs, symptoms, illnesses, events that develop or worsen in severity in association with the study when deemed by the Investigator to be related to use of the device or study procedures. The Investigator will document all adverse signs and symptoms regardless of severity or frequency that are either volunteered by subjects or observed during the course of the study that are related to the device. The Investigator will also record adverse experiences of subjects resulting from concurrent illnesses, reactions to concurrent medications, or progression of disease states that the Investigator deems related to the device. Included in the description will be the nature of the sign or symptom, the date of onset, whether the event was serious, the severity, the relationship to study procedures or investigational device, the action taken, the

 Syneron Medical Ltd. Confidential	Clinical Study to Evaluate the Safety and Efficacy of the UltraShape Power Device Using the U-Sculpt Power Transducer for Abdominal Fat and Circumference Reduction			
	Protocol #	DHF21621	Rev. Date	April 05, 2016

date of resolution, and the outcome. The Principal Investigator will determine the relationship of the adverse device effect to the investigational device.

Unanticipated Adverse Device Effects

For device studies, part 21 CFR 812.3(s) uses the term unanticipated adverse device effect which is defined as any serious adverse effect on health or safety or any life-threatening problem or death caused by, or associated with the device, if that effect, problem, or death was not previously identified in nature, severity, or degree of incidence in the investigational plan or application (including a supplementary plan or application), or any other unanticipated serious problem associated with a device that relates to the rights, safety, or welfare of subjects.

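### Delayed reactions are first looked for about 28 days after Tx.3 but about 14 days after Tx.1 and Tx.2, so short-lived ones may be missed more often after Tx.3 and delayed counts are not comparable between treatments

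*Combined protocol and SAP*

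**What the plan says.** **Timing.** Under Treatment Procedure, "Enrolled subjects will undergo 3 successive bi-weekly (2 weeks interval) treatments". Appendix I, Table 3 allows ±5 days on Tx.2 and Tx.3 but does not say whether the window runs from the previous treatment or from baseline. Under Post Treatment Procedures, "Safety aspect will be assessed before and after each treatment", so the look before Tx.2 follows up Tx.1 and the look before Tx.3 follows up Tx.2. After Tx.3, Return Visits gives the next visit as "FU1 – 4 weeks (± 7 days) post last treatment", then 8 and 12 weeks. Each return visit includes "Skin assessment for clinical effects due the procedures". No visit, call or diary is described between Tx.3 and the 4-week follow-up.

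**Endpoint.** Primary Safety Endpoint counts "The number, severity and type of any adverse event recorded throughout the study and post treatment", with immediate and delayed response both named. Its first item covers erythema and edema over the whole study period as well as immediately after treatment.

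**Capture.** The four-point Table 4 score of immediate response is taken right after each of the three treatments. The Adverse Events section covers signs and symptoms "either volunteered by subjects or observed during the course of the study" and requires dates of onset and resolution. Table 2 adds a subject interview and an adverse events form throughout the study. The Safety paragraph of Data Analysis names skin assessment by the investigator and staff as the means of evaluation. The protocol text describes no fixed list of questions about the anticipated effects.

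**The concern.** The anticipated effects are mainly local skin reactions such as purpura, bruising, blister and soreness. The Risks section reports that earlier events were mild and resolved within the study period. A mild reaction that starts a few days after treatment can be gone before anyone looks. It then enters the data only if the subject remembers and mentions it. After Tx.3 the wait until someone looks, and the period the subject must recall, are twice as long as after Tx.1 or Tx.2. Tx.3 is also the point of greatest cumulative exposure.

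Two things are at stake. The total count of short-lived delayed reactions may be too low. And if delayed reactions are tabulated by treatment, a lower count after Tx.3 could be read as good tolerance of repeat treatment when part of it reflects visit spacing.

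**Working it through.** **1. The plan's own figure.** The only stated figure that rests on these intervals is the 16-week duration in the synopsis: 2 + 2 + 12 = 16 weeks. It reproduces, so the 14-day and 28-day intervals are read as the plan intends.

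**2. Interval to the next scheduled look.**
- After Tx.1 and Tx.2: 14 days nominal. If ±5 days runs from the previous treatment: 14 − 5 = 9 to 14 + 5 = 19 days.
- If ±5 days runs from baseline, Tx.1 to Tx.2 is still 9 to 19 days, but Tx.2 to Tx.3 can be (28 − 5) − (14 + 5) = 4 to (28 + 5) − (14 − 5) = 24 days.
- After Tx.3: 28 − 7 = 21 to 28 + 7 = 35 days.

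The nominal ratio is 28/14 = 2. The ranges do not overlap under the first reading of the window and overlap slightly (21 to 24 days) under the second.

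**3. Illustration of size.** The documents give no reaction rate, duration or recall probability, so all of these are assumptions: true rate 10% after each treatment, 120 subjects (the planned maximum), onset on day 3 (after the subject has left the clinic), and exponential duration with mean m days.

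- Share still visible at day t: V(t) = exp(−(t − 3)/m).
- Share detected when a fraction r of resolved reactions is recalled: D(t) = V(t) + (1 − V(t)) × r.
- Expected detections: 120 × 0.10 × D(t) = 12 × D(t).

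For m = 14: V(14) = exp(−11/14) = 0.456 and V(28) = exp(−25/14) = 0.168. At r = 0.5, D(14) = 0.456 + 0.544 × 0.5 = 0.728, giving 8.7; D(28) = 0.168 + 0.832 × 0.5 = 0.584, giving 7.0.

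| Recall r | m = 7: Tx.1 or Tx.2 vs Tx.3 | m = 14 | m = 28 |
|---|---|---|---|
| 0 | 2.5 vs 0.3 | 5.5 vs 2.0 | 8.1 vs 4.9 |
| 0.5 | 7.2 vs 6.2 | 8.7 vs 7.0 | 10.1 vs 8.5 |
| 0.8 | 10.1 vs 9.7 | 10.7 vs 10.0 | 11.2 vs 10.6 |
| 1 | 12 vs 12 | 12 vs 12 | 12 vs 12 |

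For m = 14 the gap is 12 × (1 − r) × (0.456 − 0.168): about 3.5, 1.7, 0.7 and 0 reactions. Recall is held equal after all treatments here. If it is poorer over 28 days than over 14, the gap is wider.

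**4. Cases where the direction reverses.** If onset is spread evenly over days 0 to 28 and reactions persist, 50% have appeared by day 14 and 100% by day 28. If onset and duration are both exponential with mean about 28 days, 30% are visible at day 14 and 37% at day 28. Late or persistent reactions can therefore be counted more after Tx.3.

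**The case against.** The strongest counter-case is that the plan does not rely on examination alone. Staff interview subjects, an adverse events form is used throughout, and onset and resolution dates are required, so a resolved reaction can still be recorded. The form itself is not in the documents and may already list the anticipated effects. No comparison of reaction rates between treatments is planned: the Statistical Methods sentence "Descriptive statistics will be used to present changes in the assessments along the study course" is general and does not specify a by-treatment safety table. All of this stands, and it limits the point to a risk whose size turns on recall. It does not remove the point, because nothing described equalises the interval or discloses the difference, and a reaction that never surfaces has no dates to record.

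A reader might go further and infer that reaction rates must fall over the course because of the schedule. The documents do not support that. Immediate reactions are graded at the same time after all three treatments. The nominal intervals after Tx.1 and Tx.2 are equal, so only the step from Tx.2 to Tx.3 is affected. Tx.3 is followed by 12 weeks and three skin assessments, against about two weeks before the next treatment for Tx.1 and Tx.2.

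A reader might also compute a 2.7- to 7.4-fold loss of detection after Tx.3, from mean durations of 14 down to 7 days. That is the extreme with no recall at all. If onset is put on the treatment day, it also models reactions that staff may already have graded before the subject left. With m = 14 as above, the ratio is 8.7/7.0 = 1.24 at 50% recall and 10.7/10.0 = 1.07 at 80%.

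**Conclusion.** The point holds as a limited weakness in ascertainment of a primary safety endpoint. Short-lived reactions that begin after the subject leaves the clinic and resolve before the next visit may be missed more often after Tx.3 than after Tx.1 or Tx.2, and delayed counts are not comparable between treatments as the data would be collected. Under the assumed 10% rate, 120 subjects, day-3 onset and 14-day mean duration, the shortfall after Tx.3 is about 3.5 of 12 true reactions with no recall, 1.7 with 50% recall, 0.7 with 80% and none with full recall. The interval difference comes from the protocol. The rate, onset, duration and recall values are assumptions. Immediate reactions are not affected, and for late or persistent reactions the difference can go the other way.

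**What to change.** - **Checklist.** Before treatment at Tx.2 and at Tx.3, and at the 4-week follow-up, ask a fixed list of every anticipated effect since the last treatment. Record the onset and resolution dates that the Adverse Events section already requires. This acts on recall, the quantity that governs the gap: in the m = 14 illustration, moving from 50% to 80% recall takes detections from 8.7 to 10.7 after Tx.1 or Tx.2 and from 7.0 to 10.0 after Tx.3.
- **Reporting.** If delayed events are shown by treatment, count only those with onset before the next treatment and within a common window no longer than the shortest interval between treatments. A flat 14-day limit would not do, because the next treatment can fall as early as day 9 (or day 4 after Tx.2 if the window runs from baseline). State that examination-based rates after Tx.3 are not comparable with those after Tx.1 and Tx.2.
- **Window.** State in Table 3 what the ±5 days is measured from.
- **Optional.** A telephone check about 14 days after Tx.3, using the same checklist, would match the earlier interval.

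The cost is one CRF page, plus one short call per subject if that option is taken. Prompted questions may raise the reported count of mild events, which the report should say.

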Reporting Adverse Events (AE) and Serious Adverse Events (SAE).....	27
Measures taken to protect the rights and welfare of subject.....	27
RISK/BENEFIT ANALYSIS.....	27
Risks.....	27

 Syneron Medical Ltd. Confidential	Clinical Study to Evaluate the Safety and Efficacy of the UltraShape Power Device Using the U-Sculpt Power Transducer for Abdominal Fat and Circumference Reduction			
	Protocol #	DHF21621	Rev. Date	April 05, 2016

Potential benefits to participating individuals and to society..... 28

Conclusion: 28

ETHICS AND GOOD CLINICAL PRACTICE 28

QUALITY ASSURANCE AND STUDY MONITORING 29

 Study Monitoring/Auditing/Inspection 29

ADMINISTRATIVE PROCEDURES 29

 Supply and Disposition of Study Device 29

 Control & Disposition of the Investigational Device 29

 Informed Consent..... 30

 Monitoring Plan 30

 Case Report Forms 30

 Record Maintenance 30

PUBLICATION POLICY..... 31

BIBLIOGRAPHY 32

Appendix I – Study Summery 33

Appendix II - Scales..... 34

Appendix III - Pain assessment 35

Appendix IV - Photography..... 36

 Specific photography details: 36

 Abdomen: 36

Appendix V - Clinical Trial Acknowledgement..... 37

GLOSSARY

ADE	Adverse Device Effect
AE	Adverse Event
BMI	Body Mass Index
CFR	Code of Federal Regulations
Cm	Centimeter
CRF	Case Report Form
FDA	Food & Drug Administration
FU	Follow-up
GCP	Good Clinical Practice
ICF	Informed Consent Form
IEC	Institutional Ethics Committee
IRB	Institutional Review Board
Kg	Kilogram
Min	Minute
wk	Weeks
PI	Principal Investigator
USAE	Unanticipated, serious adverse event
USADE	Unanticipated, serious adverse device effect
SAE	Serious Adverse Event
Tx	Treatment
US	Ultrasound
W	Watt (Output Electric Power)

 Syneron Medical Ltd. Confidential	Clinical Study to Evaluate the Safety and Efficacy of the UltraShape Power Device Using the U-Sculpt Power Transducer for Abdominal Fat and Circumference Reduction			
	Protocol #	DHF21621	Rev. Date	April 05, 2016

TABLE 1- STUDY SYNOPSIS

Proprietary Name	UltraShape Power device utilizing the U-Sculpt Power Transducer
Design	
Prospective, one arm, baseline-controlled, clinical study for the evaluation of the UltraShape Power treatment using the U-Sculpt Power Transducer for non-invasive abdominal fat and circumference reduction.
 
Study subjects will undergo UltraShape Power treatments on the abdominal area

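### The protocol defines an adverse event twice, once with and once without a relatedness condition, and does not say which definition governs

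*Combined protocol and SAP*

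**What the plan says.** The combined protocol and SAP opens its Adverse Events (AE) section by defining an AE as "any adverse change in health or side effect that occurs in a study participant during their participation in the study". Nothing in that sentence refers to cause.

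Under the sub-heading Anticipated Adverse Effects, after the list of local effects, a second sentence again defines an adverse event (AE). It covers undesired clinical occurrences that arise or worsen in association with the study, but only "when deemed by the Investigator to be related to use of the device or study procedures".

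Two recording sentences follow. The first has the investigator document signs and symptoms "volunteered by subjects or observed during the course of the study that are related to the device". The second has the investigator record experiences "resulting from concurrent illnesses, reactions to concurrent medications, or progression of disease states that the Investigator deems related to the device". The same paragraph lists what is described for each event, including "whether the event was serious, the severity, the relationship to study procedures or investigational device". It closes with "The Principal Investigator will determine the relationship of the adverse device effect to the investigational device".

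The Glossary has a separate entry for "Adverse Device Effect". The Safety Endpoints row of the synopsis reads "The number, severity and type of any adverse event recorded throughout the study and post treatment (immediate and delayed response"; the Primary Safety Endpoint section has an equivalent item. Neither endpoint text adds a relatedness condition.

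**The concern.** The AE part of the primary safety endpoint counts events that are recorded, so the recording rule decides what the endpoint contains. Under the second definition, a causality judgement comes before the record is made. The person making it knows that every subject has been treated, and there is no control arm whose event rate could show whether attribution was sound. The endpoint would then hold only events that the investigator already attributes to the device or the procedures.

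Under the first definition every event is recorded and relationship is assigned afterwards, so attribution can be reviewed. With up to 10 sites and no rule of precedence, sites could choose differently, and pooled counts would mix the two rules. The subject-rated pain score and the immediate responses scored on Table 4 do not depend on the AE definition and are not affected.

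**Working it through.** No arithmetic applies: the documents attach no event rate to this text. The check is a comparison of wording.

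**1. The four sentences in the Adverse Events section**

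| Sentence | Relatedness condition | Related to what | Who judges |
|---|---|---|---|
| First definition | none | – | – |
| Second definition | yes | device or study procedures | investigator |
| First recording sentence | yes | device only | not stated |
| Second recording sentence | yes, scope ambiguous | device only | investigator |

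The condition stands in three clauses: one in the second definition and one in each recording sentence. The recording sentences are narrower than the definition they follow, because they omit study procedures. In the second recording sentence the qualifier most naturally covers all three listed sources (concurrent illness, reactions to other medication, disease progression). Grammatically it could attach to disease progression alone.

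**2. Two hypothetical events**

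*An intercurrent illness during follow-up, judged unrelated.* It is an AE under the first definition and not under the second. The first recording sentence does not capture it. The second does not on its natural reading, but does if the qualifier belongs only to disease progression.

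*Faintness from the fasting required before circumference measurement.* It is an AE under both definitions, because fasting is a study procedure. The device-only first recording sentence does not reach it.

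**3. Sections that bear on the choice**

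- *Unanticipated Adverse Device Effects* gives four relationship categories, two of which are Probably not and Not related. These sit easily with the first definition. Under the second they still have some use: they are worded against the study device, so an event due to a procedure could be rated Not related.
- *Table 2* lists relation to treatment as an item on the AE form, which suggests an attribute rather than an entry condition. It could also serve to grade events already admitted as related.
- *Post Treatment Procedures* asks for any AE before, during and after treatments. Screening may precede the first treatment by up to 14 days, and an event in that interval cannot be due to the device. It could be due to a study procedure, and an event before the second or third treatment could be due to either.
- *The endpoint texts* refer to any AE recorded. They use the defined term without redefining it, so they take on whichever definition is applied.
- *Safety*, under Data Analysis, has all complications recorded from the start of the study. That fits the broad definition, but complications may mean procedural ones.

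The first three fit the broad definition better, and none strictly excludes the narrow one. The direct contradiction is between the two definitions.

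**4. Bounds on the loss**

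- Lower bound: nil, if all sites apply the first definition.
- Upper bound: all AEs judged unrelated, if all sites apply the second definition with the natural reading of the second recording sentence.
- The upper bound also assumes that the instruction to report unanticipated adverse events to the sponsor, in the Reporting section, uses AE in the narrow sense. If it uses the broad sense, an unrelated illness outside the anticipated list is reportable. The section does not say that such reports enter the AE count.
- The 24-hour rule in the same section concerns serious unanticipated device effects. It does not by itself bring in an event judged unrelated.

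**The case against.** The strongest reply is that the second paragraph is a mislabelled adverse device effect definition. The Glossary lists that term separately and the paragraph ends on it. This may well be the intent. But the sentence names the adverse event and its abbreviation, and the recording sentences are the only ones in the section that tell the investigator what to document. If a device effect was meant, the label is wrong and still needs correcting.

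A second reply is that the rest of the protocol already shows the broad definition to be intended. That is the better reading, and it lowers the chance of harm. It does not settle the matter, because each of those sections can be read alongside the narrow definition. For the same reason, a reader might infer that the endpoint, Table 2 and the relationship categories contradict the narrow definition outright. The documents do not support that stronger reading.

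A third reply is that omitted events need not be lost. Table 2 includes subject interviews, the Recording section keeps source documents in the subject's file at the site, and the monitoring section gives monitors direct access to source. This stands in part: some events might be recovered from source. It would be wrong to say that their relatedness could never be reviewed. Recovery would depend on the site having noted the event and on someone looking for it outside the AE record.

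**Conclusion.** The point holds. The protocol gives two AE definitions that differ on whether relatedness is a condition of entry, and it does not say which governs. As written, a site could follow the second definition and its recording sentences and leave events it judges unrelated off the AE record.

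The effect on the AE counts ranges from nil to all AEs judged unrelated, and the documents do not allow an estimate within that range. The upper end rests on the assumptions set out in the comparison above.

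A reader might go further and infer that AEs will be undercounted, that sites will in fact differ, or that both recording sentences plainly exclude everything the investigator deems unrelated. The documents show none of these. They show that the counts could depend on attribution and could differ between sites. The first recording sentence does not name the investigator as judge, and the second is ambiguous in scope.

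**What to change.** Keep the first definition as the only definition of an AE, and do one of the following.

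1. Delete the second definition sentence entirely, and remove the relatedness qualifier from each of the two recording sentences. Removing only the investigator-judgement clause is not enough. The rest of that sentence still limits AEs to those arising in association with the study, so two different definitions would remain.
2. Relabel the paragraph as the definition of an adverse device effect (ADE) and add: *All AEs, whether or not related, are recorded from the start of the study.*

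In either case, assign relationship after the event is recorded, using the four existing categories, and report all AEs and related AEs separately.

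The cost is protocol wording and guidance for completing the AE form. The downside is more minor unrelated events on the CRF and a higher all-cause AE count; the separate table of related AEs keeps that count interpretable.
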